8.1. Definitions

Adverse Event (AE)

In general, AE is used very broadly and encompasses physical and psychological harms and includes:

Any untoward or unfavorable medical occurrence in a human subject, including any abnormal sign (for example, abnormal physical exam or laboratory finding), symptom, or disease, temporally associated with the subject's participation in the research, whether or not it is considered related to the subject's participation in the research.

Intercurrent illnesses or injuries should be regarded as adverse events. Abnormal results of diagnostic procedures are considered to be adverse events if the abnormality:

- results in study withdrawal
- is associated with a serious adverse event
- · is associated with clinical signs or symptoms
- leads to additional treatment or to further diagnostic tests
- is considered by the investigator to be of clinical significance

Serious Adverse Event (SAE)

Adverse events are classified as serious or non-serious. A serious adverse event is any AE that:

- results in death;
- is life-threatening (places the subject at immediate risk of death from the event as it occurred);
- results in inpatient hospitalization or prolongation of existing hospitalization;
- results in a persistent or significant disability/incapacity;
- · results in a congenital anomaly/birth defect; or
- based upon appropriate medical judgment, may jeopardize the subject's health and may require medical
 or surgical intervention to prevent one of the other outcomes listed in this definition (examples of such

0008_Protocol v2.5, 08-03-18, AMD.docx

events include allergic bronchospasm requiring intensive treatment in the emergency room or at home, blood dyscrasias or convulsions that do not result in inpatient hospitalization, or the development of drug dependency or drug abuse).

Unanticipated Problems Involving Risk to Subjects or Others (UPIRSO)

Any incident, experience, or outcome that meets all of the following criteria:

- Unexpected in nature, severity, or frequency (i.e. not described in study-related documents such as the IRB-approved protocol or consent form, the investigators brochure, etc.)
- Related or possibly related to participation in the research (i.e. possibly related means there is a reasonable possibility that the incident experience, or outcome may have been caused by the procedures involved in the research)
- Suggests that the research places subjects or others at greater risk of harm (including physical, psychological, economic, or social harm).

Adverse Event Reporting Period

The study period during which adverse events must be reported is normally defined as the period from the initiation of any study procedures to the end of the study treatment follow-up. For this study, the study treatment follow-up is defined as 7 days following the last administration of study treatment.

Pre-existing Condition

A preexisting condition is one that is present at the start of the study. A pre-existing condition should be recorded as an adverse event if the frequency, intensity, or the character of the condition worsens during the study period.

General Physical Examination Findings

At screening, any clinically significant abnormality should be recorded as a preexisting condition. At the end of the study, any new clinically significant findings/abnormalities that meet the definition of an adverse event must also be recorded and documented as an adverse event.

Abnormal Laboratory Values

A clinical laboratory abnormality should be documented as an adverse event if any one of the following conditions is met:

- The laboratory abnormality is not otherwise refuted by a repeat test to confirm the abnormality
- The abnormality suggests a disease and/or organ toxicity
- The abnormality is of a degree that requires active management; e.g. change of dose, discontinuation of the drug, more frequent follow-up assessments, further diagnostic investigation, etc.

Hospitalization, Prolonged Hospitalization or Surgery

Any adverse event that results in hospitalization or prolonged hospitalization should be documented and reported as a SAE unless specifically instructed otherwise in this protocol. Any condition responsible for surgery should be documented as an AE if the condition meets the criteria for and adverse event. Neither the condition, hospitalization, prolonged hospitalization, nor surgery are reported as an AE in the following circumstances:

- Hospitalization or prolonged hospitalization for diagnostic or elective surgical procedures for a preexisting condition.
- Surgery should not be reported as an outcome of an adverse event if the purpose of the surgery was elective or diagnostic and the outcome was uneventful.
- Hospitalization or prolonged hospitalization required to allow efficacy measurement for the study.
- Hospitalization or prolonged hospitalization for therapy of the target disease of the study, unless it is a worsening or increase in frequency of hospital admissions as judged by the clinical investigator.

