6.8. Visit 8: Post treatment measurements (7.5-8 weeks of treatment)

Subjects present in fasting state to the site CRC to assess:

- Vitals signs, weight, BMI, waist circumference
- MOCA, CES-D
- DEXA body composition, Bioimpedance (UTMB Galveston only) and Calorimetry
- Muscle biopsy (satellite cell, fiber type, fat infiltration, inflammation, gene expression)
- Blood draw: Systemic inflammation
- Drug tolerability, compliance, and AE review

See Summary of Visits Table on next page.

Summary of Visits Table

	Visit 1	Visit 2	Visit 3	Visit 4	Visit 5	Visit 6	Visit 7	Visit 8
			240		4 weeks	6-7.5	MRI	7.5-8
	Screen	MDI	V2	1 week on	on	weeks on	7-7.5	weeks on
	(fasting)	+ 7d	(fasting)	(fasting)	(fasting)	(fasting)	treatment	(fasting)
Medical history and	(raoting)		(idotilig)	(luoting)	(luoting)	(luoting)		(luoting)
physical examination.	Х							
ECG								
Vital signs, Weight, BMI	Х		Х	Х	Х	Х		Х
Waist circumference	Х			Х	Х	Х		Х
Mini-Cog	Х							
Montreal Cognitive	v				V			V
Assessment (MOCA)	~				~			~
Geriatric depression scale	V							
(GDS)	X							
Centers for Epidemiologic								
Studies Depression Scale	Х				X			Х
(CES-D)								
Gait speed, 15-foot course	Х					Х		
Electrocardiogram	Х							
**CBC. HobA1c. and								
Coagulation testing	Х					Х		
(PT/INR, PTT)								
**Chemistry with liver								
function, serum osmolality								
(other safety labs if	Х			Х	X	X		
clinically indicated by								
history)								
**Lipid Panel	Х					X		
Urinalysis	Х							
Urine osmolality	Х			Х	Х	Х		
OGTT, 2-hour	Х					Х		
Body composition (DEXA)			Х					Х
Bioimpedance (UTMB								×
only)			Х					^
Calorimetry			Х					Х
Randomization*			Х					
Body composition (MRI)		v					v	
- optional		^					^	
Functional tests: mSPPB,	v					v		
TUG, grip strength	^					^		
24-hour food recall, 3-day	v			v	×	×		
food diary, appetite	^			^	^	^		
Muscle biopsy			Х					X
Systemic inflammation			Х					Х
			AE					
			review	X	X	X		X
compliance, AE review			only					

* After Visit 4, participants may receive periodic phone calls by study staff between study visits to assess any symptoms and encourage adherence to study drug.

** Any marginally abnormal lab findings may be repeated if clinically indicated to ensure initial or continued eligibility.

7. Statistical Plan

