8.2. Recording and Reporting of Adverse Events and Protocol Deviations

At each contact with the subject, the investigator or study staff will seek information about adverse events by specific questioning and, if appropriate, by examination. The principal investigator will review the safety and progress of this study on a continuing basis. Safety data will be reviewed at each study visit. Information on all adverse events will be recorded immediately in the source document, and also in the appropriate adverse event section of the case report form.

- AEs will be tracked using the HSC IRB AE tracking form or data management tool (See Section 9.3) to be reviewed by Site Investigator weekly and IND Sponsor monthly.
- All AEs occurring during the study period will be recorded. The clinical course of each event will be followed until resolution, stabilization, or until it has been determined that the study treatment or participation is not the cause.
- All adverse events will be summarized annually and submitted to the IRB.
- Deviations from the approved protocol (PDs) will be recorded in the site Protocol Deviation Log. When a deviation occurs site investigators or research staff will notify the site IRB and the IND sponsor as appropriate per local policy and procedure.
- The IND Sponsor records every PD in a study-wide log and reviews within 48 hours of notification to determine if prompt reporting to IRB of record is required.

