8.3. Recording and Reporting of Serious Adverse Events and Unanticipated Problems

SAEs and UPIRSOs will be reported per governing IRB policy and procedure.

- UPIRSOs that are a result of study participation are reported to the IRB and the Medical Safety Officer within 24 hours. The report will include a description of the event, when and how it was reported, as well as any official chart records or documentation to corroborate the event or the reporting of the event. All adverse events will be graded as mild, moderate, or severe.
- SAEs will also be submitted to the IRB and the safety officer within 24 hours.
- SAEs that are still ongoing at the end of the study period will be followed up to determine the final outcome. Any SAE that occurs after the study period and is considered to be possibly related to the study treatment or study participation will be recorded and reported per Institutional policy and according to FDA requirements.

Any action resulting in a temporary or permanent suspension of this study (e.g. local site IRB actions) will be reported to the IND Sponsor.

Investigator reporting: notifying the IND sponsor

Any study-related UPIRSO, and any type of SAE, must be reported to IND Sponsor by telephone within 24 hours of the event. To report such events, a Serious Adverse Event (SAE) form must be completed by the investigator and faxed to IND sponsor within 24 hours. The investigator will keep a copy of this SAE form on file at the study site.

Report SAE/UPIRSOs by email or facsimile to:

[name] Associate Professor, Department of Medicine

0008_Protocol v2.5, 08-03-18, AMD.docx

OXY-SAR-001 Version: 2.5

> University of Texas Health Science Center at San Antonio Barshop Institute for Longevity and Aging Studies [name] [contact] (phone) – [contact] (fax) Email: [contact]

Within the following 48 hours, the investigator must provide further information on the SAE or the UPIRSO in the form of a written narrative. This should include a copy of the completed SAE form, and any other diagnostic information that will assist the understanding of the event.

Reporting Process: Notifying the UTHSCSA IRB

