8.6. Stopping Rules

In the unlikely event that a study-related death or SAE occurs, the decision to stop the trial, either temporarily or permanently, will be the responsibility of the Medical Safety Officer in collaboration with the IND Sponsor.

Clinical excursions that a subject may experience that may warrant stopping study participation or drug administration either temporarily or permanently include but are not limited to:

- Clinical criteria:
 - Fever with a temperature > 101°F or other clinical indication of active illness
 - Blood pressure >170/95 or <90/50
 - Allergic reaction to drug
 - Serious nosebleeds or other localized side effects of drug administration
 - Hyponatremia (serum sodium < 135 mmol/L) and/or low serum osmolality (serum osmolality < 275 mOsm/kg).
 - Obtain serum sodium levels and osmolality at any time hyponatremia is suspected based on symptoms lethargy, muscle spasms, seizures, confusion/delirium, nausea and vomiting or physical examination
 - Any patient withdrawn from the study or has low sodium levels at the final visit will be evaluated until full normalization of the electrolyte abnormality occurs, and clinical and laboratory evaluations will be made available to medical safety monitor for review.
 - Other Serious Adverse Event adjudicated by medical safety monitor and invoking stopping rules

9. Data Handling and Record Keeping

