ATTACHMENT B. EVENT SCHEDULE

	Visit 1	Visit 2	Visit 3	Visit 4*	Visit 5	Visit 6	Visit 7	Visit 8
	Screen Day 0	MRI +7 days	V2 +7-14 days	1 week on Rx	4 weeks on Rx	6-7.5 weeks on Rx	7-7.5 weeks on Rx	7.5-8 weeks on treatment
Medical history and physical examination, ECG	х							
Vital signs, Weight, BMI,	Х		x	Х	X	X		x
Waist circumference	х			Х	х	x		x
Mini-mental status exam (Mini- Cog)	х							
Montreal Cognitive Assessment (MoCA)	х				x			х
Geriatric depression scale (GDS)	х							
Centers for Epidemiologic Studies Depression Scale	Х				х			Х
Gait speed, 15-foot course	Х					Х		
**Hematology (CBC, HgbA1c) and Coagulation testing (PT/INR, PTT)	х					х		
**Chemistry with liver function and serum osmolality	Х			Х	х	х		
**Lipid Panel	Х					Х		
**Urinalysis	Х							
**Urine osmolality	Х			Х	Х	Х		
Electrocardiogram	Х							
OGTT, 2 hour	Х					Х		
Body composition (DEXA)			X					Х
Bioimpedance (UTMB only)			X					Х
Calorimetry			X					Х
Randomization			X					
Body composition (MRI)		Х	Х				Х	
Functional tests: mSPPB, TUG, grip strength	х					х		
24-hour food recall, 3-day food diary, appetite	х			Х	х	х		
Muscle biopsy: satellite cell, fiber type, fat infiltration, inflammation, gene expression			x					Х
Systemic inflammation			Х					Х
Drug tolerability/ compliance, adverse event monitoring			AE review only	X	X	X		X

* After Visit 4, participants may receive periodic phone calls by study staff between study visits to assess any symptoms and encourage adherence to study drug.

** Any marginally abnormal lab findings may be repeated if clinically indicated to ensure initial or continued eligibility.

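### Adverse events are reportable until 7 days after the last dose, but no contact with completers is scheduled after Visit 8, which falls on treatment and is the day of the second muscle biopsy

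*Combined protocol and SAP*

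**What the plan says.** The reporting period in section 8.1 runs from the first study procedure to the end of treatment follow-up, which is then defined: "For this study, the study treatment follow-up is defined as 7 days following the last administration of study treatment". Section 8.2 describes how events are found: "At each contact with the subject, the investigator or study staff will seek information about adverse events by specific questioning".

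The last scheduled contact for a completer is headed "Visit 8: Post treatment measurements (7.5-8 weeks of treatment" in section 6.8, and Attachment B labels the same column "7.5-8 weeks on treatment". The visit includes an adverse-event review, DEXA and the second vastus lateralis biopsy. Nothing follows it in section 6, in the Summary of Visits Table or in Attachment B, and the payment table in section 12.3 ends there too. The footnote to both schedules says that, after Visit 4, "participants may receive periodic phone calls by study staff between study visits to assess any symptoms and encourage adherence to study drug".

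Several provisions reach past Visit 8:
- Section 8.2, for recorded events: "The clinical course of each event will be followed until resolution, stabilization".
- Section 8.3, for serious events: "SAEs that are still ongoing at the end of the study period will be followed up to determine the final outcome". Later serious events judged possibly related are also to be reported.
- Section 8.6, for a subject with "low sodium levels at the final visit will be evaluated until full normalization of the electrolyte abnormality occurs".
- Section 10.1 has the monitor search research records for missed events.

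**The concern.** A reporting window yields data only if someone asks during it or the subject comes forward. Under section 8.2, asking is tied to contacts, and the schedule provides none for completers in the last week of the window. Serious events would probably surface anyway. Mild ones, such as a bruise or numb patch at the biopsy site, or symptoms after stopping the spray, are the kind that people often mention only when asked.

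The timing of the biopsy sharpens the point. The first biopsy, at Visit 3, is followed by a tolerability and side-effect assessment at Visit 4, about one week after drug is started. The second has no such check. What is at stake is the completeness of the count of non-serious events in a small study of adults aged 60 or older.

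**Working it through.** The plan has no calculated figure of its own to reproduce here, so the check is a timeline, a count, and a reading of what the other provisions cover.

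**Inputs**
- Dosing: 56 days (section 5.2).
- Visit 8: 7.5 to 8 weeks on treatment (section 6.8, Attachment B).
- Follow-up for adverse events: 7 days after the last dose (section 8.1).
- Completers: 36; ceiling of 15 subjects at each of 3 sites (Study Summary, section 7.1).
- Biopsy rates: local hematoma in under 2% of subjects; transient altered sensation in about 1 in 50 (section 3.4).

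**Uncovered days per completer** = (day of last dose + 7) − day of Visit 8
- Visit 8 falls between day 7.5 × 7 = 52.5 and day 8 × 7 = 56.
- Dosing stops at Visit 8: 7 days, whenever the visit falls.
- Dosing runs to day 56: the window closes on day 56 + 7 = 63. The gap is 63 − 56 = 7 days for a visit at 8 weeks and 63 − 52.5 = 10.5 days for a visit at 7.5 weeks.

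**Subject-days without a scheduled enquiry**
- 36 × 7 = 252
- 36 × 10.5 = 378

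Each is a ceiling for its dosing assumption. A subject with an event still open at Visit 8 is followed further under section 8.2 and would be questioned at that contact.

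**Events expected from the second biopsy in 36 completers**
- Hematoma: fewer than 36 × 0.02 = 0.72
- Altered sensation: about 36 × 1/50 = 0.72

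These are totals for the procedure. Some would be evident at the visit itself, so the number arising unseen is smaller. For drug effects, section 3.4 gives frequencies but no onset times, so the number beginning in this week cannot be derived.

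**Do the other provisions close the gap?**
- Follow-up under section 8.2 and the ongoing-event clause of section 8.3 start from an event already known.
- The late-event clause of section 8.3 concerns serious events only and schedules no contact.
- The sodium clause in section 8.6 needs a low value at the final visit or a withdrawal. Neither schedule marks chemistry at Visit 8; the last routine sample is at Visit 6.
- The monitor's review (section 10.1) takes place once per site and covers 30% of subject records. It can find only events that left a trace.
- The closing examination in section 4.4.1 is for subjects who withdraw.
- The footnote calls are optional and fall between visits, so they do not extend beyond the last one.

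None of these actively seeks new non-serious events in a completer after Visit 8.

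**The case against.** The best defense is that section 8.1 sets a duty to report and promises no closing enquiry. Section 8.2 requires every event in the study period to be recorded, so anything a subject volunteers in that week must be entered. On that reading the document does not contradict itself, and relying on passive capture for one week is a choice. This stands, and it is why the point is an improvement rather than an error.

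A second objection is that the yield is small. This also stands: the biopsy figures are below one event of each kind, and events from the first biopsy are already asked about at Visit 4.

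Third, the dosing-end question may look larger than it is. The heading of section 6.8 refers to measurements after treatment, and the v2.1 entry in Attachment E pairs completion of study drug with the final visit. The intent is reasonably clear that dosing ends at about Visit 8, which favors the 7-day figure. The 10.5-day figure is the outer case if the 56 days in section 5.2 are taken literally.

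Fourth, a closing contact may be specified elsewhere. Section 8.4 was not in the text available for review, the consent form and instruments appear only as placeholders, and section 9.3 mentions a Manual of Operations. The calendar also leaves room for one: randomization on day 21, plus 56 days of dosing and 7 of follow-up, makes 84 days, exactly the 12 weeks in the Study Summary. That suggests the week was planned for, but both visit schedules are complete and attach no contact to it.

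**Conclusion.** The point holds as a minor one. For completers, the last 7 days of the protocol's own reporting period have no scheduled enquiry. The gap reaches 10.5 days if Visit 8 is at 7.5 weeks and dosing continues to day 56. Over 36 completers this is 252 to 378 subject-days, and new events in that time, mostly non-serious, depend largely on the subject volunteering them.

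A reader might infer more, and the documents do not support it:
- *That safety follow-up stops at Visit 8.* It does not. Known events, ongoing serious events and low sodium are all followed, and late related serious events are reportable.
- *That the arms are compared unfairly or the efficacy results are affected.* Both arms follow the same schedule, and no efficacy outcome is measured after Visit 8.
- *That a material number of events would be missed.* The biopsy rates point to very few, and the documents do not allow a count for drug effects.

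The conclusion assumes that no closing contact is set out in the material that could not be seen, so confidence is moderate.

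**What to change.** Add one telephone adverse-event contact, at least 7 days after the last dose, to section 6, the Summary of Visits Table and Attachment B. At the call, record the date of the last dose and ask about drug effects and the biopsy site. So that staff know when the call is due, add a sentence to sections 5.2 and 6.8 saying whether dosing ends at Visit 8 or on day 56. If the Manual of Operations already provides such a call, it is enough to enter it in both schedules.

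The cost is a short amendment and about 36 calls for the planned completers, or at most 3 × 15 = 45 at the enrollment ceiling. No new visit, procedure or staff is needed, and sample size and power do not change.

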8.2. Recording and Reporting of Adverse Events and Protocol Deviations

At each contact with the subject, the investigator or study staff will seek information about adverse events by specific questioning and, if appropriate, by examination. The principal investigator will review the safety and progress of this study on a continuing basis. Safety data will be reviewed at each study visit. Information on all adverse events will be recorded immediately in the source document, and also in the appropriate adverse event section of the case report form.

- AEs will be tracked using the HSC IRB AE tracking form or data management tool (See Section 9.3) to be reviewed by Site Investigator weekly and IND Sponsor monthly.
- All AEs occurring during the study period will be recorded. The clinical course of each event will be followed until resolution, stabilization, or until it has been determined that the study treatment or participation is not the cause.
- All adverse events will be summarized annually and submitted to the IRB.
- Deviations from the approved protocol (PDs) will be recorded in the site Protocol Deviation Log. When a deviation occurs site investigators or research staff will notify the site IRB and the IND sponsor as appropriate per local policy and procedure.
- The IND Sponsor records every PD in a study-wide log and reviews within 48 hours of notification to determine if prompt reporting to IRB of record is required.

